### 8.5 Visit Windows

Study visits should take place within the time limits specified as follows:

The visit window between the screening DBPCFC and Visit 1 is 14 days. The visit window for Visits 1-9 and SU visit is -7 to +14 days. The visit window for the Desensitization DBPCFC visit is -7 days to 6 months. Due to the uncertainty of the COVID-19 pandemic and the challenges with in-person visits, a large window is necessary to provide sufficient opportunity for subjects to return for the primary endpoint visit. For participants who pass this 6 month window by the time this version of the protocol has been approved, an extension of the window will be applied. If a visit window is missed for visits 2-9, the escalation will be skipped and addressed at the next scheduled escalation visit. An exception is for visits 2-9 that cannot be undertaken for study pause for COVID or similar reasons in which case the visit window is not considered and the study visits resume when possible in the planned sequence. When face to face visits resume after a pause, the visit window period to resume an in-person visit from approval to restart is extended to 8 weeks to allow safe scheduling and ramp-up study restart. After the 8 week period, windows resume.

### Table 2. Table of Events (does not include unscheduled visits)

Procedures	Screening /Baseline DBPCFC week 0, 3 days	Visit #1. Initial feeding with sub-threshold amount, week 1	Visit 2-9, evaluate to increase threshold, week 8,16, 24, 32, 40, 48, 56, 64 (all visits may not be needed depending upon escalation progress)	DBPCFC for desensitizatio n (active) or follow up (controls) Week 32, 56, 64 or 72	SU DBPCFC (24 weeks after desensitization DBPCFC for those on active peanut
Informed consent, screening, complete	All				

Procedures	Screening /Baseline DBPCFC week 0, 3 days	Visit #1. Initial feeding with sub-threshold amount, week 1	Visit 2-9, evaluate to increase threshold, week 8,16, 24, 32, 40, 48, 56, 64 (all visits may not be needed depending upon escalation progress)	DBPCFC for desensitizatio n (active) or follow up (controls) Week 32, 56, 64 or 72	SU DBPCFC (24 weeks after desensitization DBPCFC for those on active peanut
medical history, demographic questions					
Physical assessment, vital signs, spirometry, interval medical assessment	All	Intervention group	Intervention group	All	Intervention group passing desensitization
Pregnancy test (urine) for females of child bearing potential	All			All	Intervention group passing desensitization
DBPCFC as per PRACTALL protocol, up to cumulative dose 9043	All			All	Intervention group passing desensitization
Open peanut feeding for threshold		Intervention group	Intervention group		
Skin prick testing	All			All	Intervention group passing desensitization
Blood sample , stool and saliva collection	All		All, week 16	All	Intervention group passing desensitization
Quality of life questionnaire, diet survey	All		All week 16	All	Intervention group passing desensitization
Review adverse events and home food administration diary, report all			All (including monthly call [monthly review call not	All	Intervention group passing desensitization

Procedures	Screening /Baseline DBPCFC week 0, 3 days	Visit #1. Initial feeding with sub-threshold amount, week 1	Visit 2-9, evaluate to increase threshold, week 8,16, 24, 32, 40, 48, 56, 64 (all visits may not be	DBPCFC for desensitizatio n (active) or follow up (controls) Week 32, 56, 64 or 72	SU DBPCFC (24 weeks after desensitization DBPCFC for those on active peanut
			depending upon		
			escalation		
			progress)		
food allergic			performed if		
reactions (both			an in-person		
randomized groups)			visit occurs;		
			monthly calls		
			continue until		
			last study		
			visit]).		

# 9 Mechanistic Assays

Peripheral blood will be collected in sodium heparin tubes to obtain whole blood, plasma, and cells. A whole blood aliquot will be stored at -80C, tubes will then be centrifuged to obtained plasma, and the remaining cellular fraction used for basophil activation and T cell assays. For biomarker identification, additional blood will be obtained in Tempus tubes for RNA isolation. This will be followed by library preparation and RNA sequencing. DNA may be isolated from selected whole blood aliquots for genotype determination by array.

Plasma will be aliquoted and stored in cryovials at -80 C until use. An aliquot of blood (1 ml) will be used fresh for basophil activation tests. Briefly, whole blood will be stimulated with peanut extract or anti-IgE or fMLP as positive controls. Blood will be stained, fixed, and acquired by flow cytometry. Additional blood will be stimulated and cryopreserved for mass cytometry.

The remaining cellular fraction will undergo ficoll separation for purification of PBMCs, which will be cryopreserved until use in batched stimulations.

To assess T cell frequency and phenotype, PBMCs will be thawed, rested overnight, and stimulated with peanut antigen in the presence of Brefeldin A. After 6h, cells will be harvested. Peanut-responsive cells will be identified by upregulation of CD154 and CD137. Intracellular cytokines and surface markers will be used to identify T cell subsets.

### **10** Biospecimen Storage

Whole blood aliquots, plasma and Tempus tubes will be stored at -80 until use. Freezers are on emergency backup power and monitored by alarm system that alerts lab staff by phone call.

Cryopreserved PBMCs will be stored in alarm-monitored liquid nitrogen tank.

# 11 Criteria for Participant and Study Completion and Premature Study Termination

### **11.1** Participant Completion

Participants will be considered to have completed the protocol if they completed the desensitization DBPCFC visit, or if they were in the active arm and tolerated peanut at desensitization DBPCFC and underwent evaluation for SU at final study visit.

The statistical analysis plan allows for inclusion of non-completers (Section 13).

### **11.2** Participant Stopping Rules

Participants may be prematurely terminated from the study for the following reasons:

- 1. The participant elects to withdraw consent from all future study activities, including follow-up.
- 2. The participant is "lost to follow-up" (i.e., no further follow-up is possible because attempts to reestablish contact with the participant have failed).
- 3. The participant dies.
- 4. The Investigator no longer believes participation is in the best interest of the participant. This includes subjecs who refuse to come for the Desensitization DBPCFC visit.
- 5. Pregnancy
- 6. Subjects who fail to adhere to the request to stop the study intervention per section 6.5 will be considered for premature termination. Development of eosinophilic esophagitis

### **11.3** Participant Replacement

Participants who withdraw or are withdrawn will not be replaced and will be part of the ITT analysis.

### **11.4** Follow-up after Early Study Withdrawal

See section 8.4.

### 11.5. Study Stopping Rules

# There are no pre-specified study stopping rules, but study procedures and dosing will be temporarily suspended pending DSMB review (see 12.8.2.2.1) for the following reasons:

- Any death possibly related to study participation.
- 2 subjects requiring more than 1 injection of epinephrine during at-home, ingestion of study-allowed peanut.
- 3 subjects diagnosed with eosinophilic esophagitis

### **12** Safety Monitoring and Reporting

### 12.1 Overview

This section defines the types of safety data that will be collected under this protocol and outlines the procedures for appropriately collecting, grading, recording, and reporting those data. Adverse events that are classified as serious according to the definition of health authorities must be reported promptly (per Section 12.5, *Reporting of Serious Adverse Events and Adverse Events*) to the Sponsor-investigator, NIAID medical monitor, and Sponsor medical monitor. Appropriate notifications will also be made to site principal investigators, Institutional Review Boards (IRBs), and health authorities.

Information in this section complies with ICH Guideline E2A: Clinical Safety Data Management: Definitions and Standards for Expedited Reporting, ICH Guideline E-6: Guideline for Good Clinical Practice, 21CFR Parts 312 and 320, and applies the standards set forth in the National Cancer Institute (NCI), Common Terminology Criteria for Adverse Events (CTCAE), Version 5.0 : http://ctep.cancer.gov/reporting/ctc.html.

### 12.2 Definitions

### 12.2.1 Adverse Event (AE)

Any untoward or unfavorable medical occurrence associated with the subject's participation in the research, whether or not considered related to the subject's participation in the research (modified from the definition of adverse events in the 1996 International Conference on Harmonization E-6 Guidelines for Good Clinical Practice) (from OHRP "Guidance on Reviewing and Reporting Unanticipated Problems Involving Risks to Subjects or Others and Adverse Events (1/15/07)" http://www.hhs.gov/ohrp/policy/advevntguid.html#Q2)

For this study, any adverse event will be assessed for relationship during the following times frames with:

- **Study therapy regimen**: Ingestion of sub-threshold amounts of home-measured, home-purchased peanut. AEs will be collected until study completion or withdrawal.
- **Study mandated procedures**: AEs associated with DBPCFC, blood draw, observed feedings, skin prick tests will be monitored for 24 hours after the procedure.

### 12.2.1.1 Suspected Adverse Reaction (SAR)

Any adverse event for which there is a reasonable possibility that the investigational drug [or investigational study therapy regimen] caused the adverse event. For the purposes of safety reporting, 'reasonable possibility' means there is evidence to suggest a causal relationship between the drug and the adverse event. A suspected adverse reaction implies a lesser degree of certainty about causality than adverse reaction, which means any adverse event caused by a drug (21 CFR 312.32(a)).

### 12.2.2 Unexpected Adverse Event

An adverse event or suspected adverse reaction is considered "unexpected" if it is not listed in the protocol, or Informed Consent Forms or is not listed at the specificity, severity or rate of occurrence that has been observed; or, is not consistent with the risk information described in the general investigational plan or elsewhere.

### 12.2.3 Serious Adverse Event (SAE)

An adverse event or suspected adverse reaction is considered "serious" if, in the view of either the investigator or Sponsor-Investigator, it results in any of the following outcomes (21 CFR 312.32(a)):

- 1. Death.
- 2. A life-threatening event: An AE or SAR is considered "life-threatening" if, in the view of either the investigator or Sponsor-Investigator its occurrence places the subject at immediate risk of death. It does not include an AE or SAR that had it occurred in a more severe form, might have caused death.
- 3. Inpatient hospitalization or prolongation of existing hospitalization.
- 4. Persistent or significant incapacity or substantial disruption of the ability to conduct normal life functions.
- 5. Congenital anomaly or birth defect.
- 6. Important medical events that may not result in death, be life threatening, or require hospitalization may be considered serious when, based upon appropriate medical judgment, they may jeopardize the subject and may require medical or surgical intervention to prevent one of the outcomes listed above.

# 12.3 Grading and Attribution of Adverse Events

# 12.3.1 Grading Criteria

The study site will grade the severity of adverse events experienced by the study subjects according to the criteria set forth in the National Cancer Institute's Common Terminology Criteria for Adverse Events (NCI-CTCAE, 5.0), with the exception of anaphylaxis which will be graded according to the scale included in the definition section This document (referred to herein as the NCI-CTCAE manual) provides a common language to describe levels of severity, to analyze and interpret data, and to articulate the clinical significance of all adverse events. The NCI-CTCAE has been reviewed by the PI/Co-I and has been deemed appropriate for the subject population to be studied in this protocol.

Adverse events will be graded on a scale from 1 to 5 according to the following standards in the NCI-CTCAE manual:

Grade 1 = mild adverse event.

Grade 2 = moderate adverse event.

Grade 3 = severe and undesirable adverse event.

Grade 4 = life-threatening or disabling adverse event.

Grade 5 = death.

Only events grade 2 or higher and SAEs will be recorded on the appropriate AE case report form for this study.

For grading an abnormal value or result of a clinical or laboratory evaluation (including, but not limited to, a radiograph, an ultrasound, an electrocardiogram etc.), a treatment-emergent adverse event is defined as an increase in grade from baseline or from the last post-baseline value that doesn't meet grading criteria. Changes in grade from screening to baseline will also be recorded as adverse events, but are not treatment-emergent. If a specific event or result from a given clinical or laboratory evaluation is not included in the NCI-CTCAE manual, then an abnormal result would be considered an adverse event if changes in study therapy or monitoring are implemented as a result of the event. For additional information and a printable version of the NCI-CTCAE manual, consult the NCI-CTCAE web site: http://ctep.cancer.gov/reporting/ctc.html.

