# **Study Definitions Page**

1. Anaphylaxis	Anaphylaxis is a generalized allergic reaction that is rapid in onset and may progress to death.1		
2. Criteria for anaphylaxis	Anaphylaxis is likely when any one of the three following sets of criteria are fulfilled:		
anapriyiaxis	1. Acute onset of an illness (minutes to hours) with involvement of:		
	
 
Skin/mucosal tissue (e.g., generalized hives, itch or flush, swollen lips/tongue/uvula) AND
 
		
	
 
Airway compromise (e.g., dyspnea, stridor, wheeze/ bronchospasm, hypoxia, reduced PEF) AND/OR
 
		
	
 
Reduced BP or associated symptoms (e.g., hypotonia, syncope, incontinence)
 
		
	2. Two or more of the following that occur rapidly after exposure to a likely allergen for that patient (minutes to hours):		
	
 
Skin/mucosal tissue (e.g., generalized hives, itch/flush, swollen lips/tongue/uvula)
 
		
	
 
Airway compromise (e.g., dyspnea, stridor wheeze/bronchospasm, hypoxia, reduced PEF)
 
		
	
 
Reduced BP or associated symptoms (e.g., hypotonia, syncope, incontinence)
 
		
	
 
Persistent GI symptoms (e.g., nausea, vomiting, crampy abdominal pain)
 
		
	3. Reduced BP after exposure to known allergen for that patient (minutes to hours):		
	
 
Infants and Children: low systolic BP (age-specific) or >30% drop in systolic BP*
 
		
	• Adults: systolic BP <90 mm Hg or >30% drop from their baseline		
	* Low systolic BP for children is defined as <70 mmHg from 1 month to 1 year; less than (70 mmHg + [2 x age]) from 1-10 years; and <90 mmHg from age 11-17 years.		

3. Anaphylaxis grading	Grading System of Severity of Anaphylaxis		
	Grade	Defined By	
	1. Mild (skin & subcutaneous tissues, GI, &/or mild respiratory)	Flushing, urticaria, periorbital or facial angioedema; mild dyspnea, wheeze or upper respiratory symptoms; mild abdominal pain and/or emesis	
	2. Moderate (mild symptoms + features suggesting moderate respiratory, cardiovascular or GI symptoms)	Marked dysphagia, hoarseness, and/or stridor; SOB, wheezing & retractions; crampy abdominal pain, recurrent vomiting and/or diarrhea; and/or mild dizziness	
	3. Severe (hypoxia, hypotension, or neurological compromise)	Cyanosis or SpO2 < 92% at any stage, hypotension, confusion, collapse, loss of consciousness; or incontinence	
	4. Life-threatening	The above, and cardiac or respiratory arrest	
	5. Death		

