### AADCRC

regimens induce desensitization purposefully in an escalation phase rather than providing ingestion amounts known to be tolerated at presentation, and 3) permit dosing despite chronic symptoms. If extrapolation is accepted nonetheless, then the intervention (allowance of home ingestion of a tolerated amount) could be considered similar to the "maintenance phase" of peanut OIT. Most reactions to peanut OIT occur in the "escalation" or "build-up" phases. However, anaphylaxis rates are 0.01% across studies. In a representative study, the risk of dosing symptoms to peanut was 93% during the escalation day, 46% during build-up, but only 3.5% for final home dosing. Most of those symptoms were upper respiratory (1.2%), skin (1.1%) and abdominal (0.9%) with 0.3% affecting the chest (mild in 0.2%, moderate in 0.06%, none severe). These observations speak to the stability of a threshold even for those with a low peanut allergy threshold.

Having food allergy is a risk for eosinophilic esophagitis (EoE) and ingestion of ostensibly tolerated foods (i.e., no acute reaction) can be a trigger (most common triggers are milk and wheat). The risk that OIT can trigger EoE has been estimated at up to 2.7%. This risk will also be communicated to potential participants. Participants will be monitored for new onset of persistent gastrointestinal symptoms and or weight loss and if EoE is suspected they will be instructed to discuss this with their allergist or pediatrician for potential referral to a pediatric gastroenterologist for evaluation outside of the study, if necessary. Therapy will be stopped in case of new onset EoE; pre-existing EoE is an exclusion criterion.

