### 6.3 Assessment of Participant Compliance with Investigational Agent

All participants will be instructed to avoid peanut, except for the subthreshold amount allowed for ingestion by those randomized to the intervention. Symptom diaries will be monitored and all allergic reactions reported. Serum peanut-specific IgG will be measured as a potential marker of exposure which will be queried further if noted in the avoidance arm (i.e., drop-in to intervention).

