### **12.4.3** Recording Adverse Events

Throughout the study, the investigator will record adverse events and serious adverse events as described previously (Section 12.2, Definitions) on the AE/SAE eCRF regardless of the relationship to study therapy regimen or study procedure.

The investigator will treat subjects experiencing AEs appropriately and observes them at suitable intervals until their symptoms resolve or stabilize. Once recorded, an AE/SAE will be followed until it resolves with or without sequelae, or until the end of study participation, or until 30 days after the subject prematurely withdraws (without withdrawing consent)/or is withdrawn from the study, whichever occurs first.

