5.2 Secondary Clinical Endpoints

The following secondary clinical endpoints will be assessed:

- 1. Sustained unresponsiveness (intervention group) or natural tolerance (control group; attaining tolerance without an intervention)
- 2. Safety parameters (acute allergic reactions, including anaphylaxis, gastrointestinal side effects)
- 3. Quality of life measures
- 4. Skin prick test mean wheal size

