6.5.2.4 Adverse Events

Individual adverse events will be summarized as the number (%) of events and number and (%) of patients with the event in peanut ingestion and avoidance subjects. Adverse events will be modelled using Poisson regression and the rate of individual adverse events will compared between randomization arms through the desensitization DBPCFC visit. Long-term adverse events will be evaluated for those in the intervention group who are tested for sustained unresponsiveness following the desensitization DBPCFC visit. The Safety population will be used for this analysis.

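### The protocol's recording rules conflict on grade 1 events, and the SAP does not say whether mild allergic reactions enter the between-arm safety comparison

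*Protocol*

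**What the plan says.** **Recording.** Protocol 12.3.1 states: "Only events grade 2 or higher and SAEs will be recorded on the appropriate AE case report form for this study". It grades by CTCAE, "with the exception of anaphylaxis which will be graded according to the scale included in the definition section". On that scale, in the Study Definitions, grade 1 reads: "Flushing, urticaria, periorbital or facial angioedema; mild dyspnea, wheeze or upper respiratory symptoms; mild abdominal pain and/or emesis". Protocol 12.4.3 gives a different rule: "the investigator will record adverse events and serious adverse events as described previously (Section 12.2, Definitions) on the AE/SAE eCRF". The adverse event definition in 12.2.1 has no severity threshold.

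**Endpoint.** SAP 5.2, like Protocol 3.3.1 and 13.2, lists as a secondary endpoint "Safety parameters (acute allergic reactions, including anaphylaxis, gastrointestinal side effects". No grade limit is attached.

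**Analysis.** SAP 6.5.2.4 states: "Adverse events will be modelled using Poisson regression and the rate of individual adverse events will compared between randomization arms", up to the desensitization challenge. It names neither the form nor a grade range.

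**Other collection.** Protocol 6.3 says: "Symptom diaries will be monitored and all allergic reactions reported". Under Protocol 8.3, participants in both arms keep diaries covering any reaction or symptom. These are reviewed monthly and documented on an eCRF or as an email printout. Table 2 also asks for every food-allergic reaction in both arms to be reported.

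**The concern.** Safety relative to avoidance is one of the trial's stated hypotheses (Protocol 2.1 and 13.6). The novel risk is home ingestion, where a mild reaction still has consequences: Protocol 8.4 allows it to lead to a repeat visit or a reduced amount.

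If the grade 2 floor is applied and the adverse event form feeds the analysis, a child with generalised hives and mild wheeze after a home dose can meet the study's own criteria for anaphylaxis and still not be counted, unless the event is judged serious. The absolute reaction count would then be too low for an endpoint defined without a floor.

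Investigators know the allocation (Protocol 3.4). Under the floor, their judgement between grade 1 and grade 2 would decide whether an event is counted at all. If staff follow 12.3.1 for some events and 12.4.3 for others, the count has no fixed meaning.

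**Working it through.** The plan states no figure for this point, so there is none to reproduce. The check is mainly a comparison of text.

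**Step 1: can anaphylaxis be grade 1 and fall below the floor?** The first anaphylaxis criterion in the Study Definitions is met by acute skin or mucosal involvement together with airway compromise, wheeze included. The grade 1 row contains both urticaria and mild wheeze. The floor sentence in 12.3.1 makes no exception for anaphylaxis, only for SAEs. So the answer is yes, when the event is not serious.

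**Step 2: what reaches the comparison?** This depends on two things that the documents leave open.

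| Rule followed | Source used for SAP 6.5.2.4 | Grade 1 reactions |
|---|---|---|
| 12.3.1 | adverse event form | left out unless serious |
| 12.4.3 | adverse event form | included |
| either | diary and monthly review | included if entered on an eCRF; not directly analysable if held as an email printout |

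The form is the more likely source. Attribution is recorded there (Protocol 12.3.2), and Protocol 13.4.4 says that the analysed events are CTCAE-coded. That is an inference; the SAP does not say it.

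**Step 3: does another analysis fill the gap?** SAP 6.5.3.1 compares severity scores between arms, but only for reactions during food challenges. Protocol 13.4.6 lists allergic reactions among items to be described, without a source, a grade range or a comparison. Neither is a between-arm analysis of reactions at home.

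**Step 4: can the number affected be estimated?** The only severity split for home dosing is in Protocol 5.2, from a cited oral immunotherapy study: "0.3% affecting the chest (mild in 0.2%, moderate in 0.06%, none severe".

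- Mild share of chest symptoms: 0.2 / (0.2 + 0.06) = 77%, or 0.2 / 0.3 = 67% on the stated total.
- The study's symptom rates are 1.2% upper respiratory, 1.1% skin, 0.9% abdominal and 0.3% chest, which sum to 3.5%. The three types without a severity split make up (1.2 + 1.1 + 0.9) / 3.5 = 91% of that total.

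The following is an illustration only. It assumes 36 children dosing daily with no discontinuation, the 3.5% read as a per-dose rate, and 32 to 72 weeks (the range of expected times in Protocol 13.3):

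- 32 weeks: 36 × 32 × 7 = 8,064 doses; × 0.035 = about 282 symptomatic doses.
- 72 weeks: 36 × 72 × 7 = 18,144 doses; × 0.035 = about 635 symptomatic doses.
- With an assumed mild share of 50% to 90%, a grade 2 floor keeps 282 × 0.5 = 141 down to 282 × 0.1 = 28 at 32 weeks, and 635 × 0.5 = 318 down to 635 × 0.1 = 64 at 72 weeks.

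A span of 28 to 318 retained events shows that the documents cannot size the effect.

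**The case against.** The strongest reply is that nothing has been shown to be lost. Section 12.4.3 has no grade limit, the SAP does not tie its comparison to a floor, and reactions of every grade are collected in both arms. A grade 1 event judged serious would be recorded even under 12.3.1. Any floor applies equally to both arms, events of grade 2 and above remain countable, secondary p-values are descriptive (SAP 6.6), and no rule for declaring the approach safe hangs on this count.

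Most of this stands, and it rules out two stronger inferences that a reader might draw. One is that the plan certainly drops grade 1 events. The documents do not support that, because two recording rules compete and the data source is unnamed. The other is that the missing events are most of the safety endpoint. That would rest on the 77% figure, which covers chest symptoms only, equates that study's mild category with this trial's grade 1, and comes from a different population. Protocol 5.2 itself cautions against carrying oral immunotherapy risks over to this intervention.

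The reply does not remove the gap. If 12.3.1 is taken to govern as the more specific rule, the form excludes events that the endpoint includes. If 12.4.3 governs, the floor sentence is wrong. Collection in diaries does not help the comparison unless the SAP uses them and the entries are analysable. An equal floor leaves a rate ratio unchanged only if the mild share is the same in both arms; the counts, and any difference in rates, still shrink.

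**Conclusion.** The point holds as an unreconciled recording rule and an undefined analysis source for an endpoint that has no grade limit. Under Protocol 12.3.1, with the adverse event form as the source, non-serious grade 1 anaphylaxis and mild allergic and gastrointestinal reactions are left out of the between-arm comparison. Under 12.4.3, or with diary data in structured form, they are not.

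The size is unknown. The counts in the working rest on an outside per-dose rate, full adherence and an assumed mild share, and should not be read as an estimate for this trial. Correcting this is a cheap improvement to the plan; no loss of data has been demonstrated.

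**What to change.** 1. Reconcile Protocol 12.3.1 and 12.4.3 so that allergic reactions and anaphylaxis of any grade are recorded in analysable form in both arms, whatever floor is kept for other events. An email printout should not be the only record of a reaction.
2. In SAP 6.5.2.4, name the data source and grade range. Compare all-grade acute allergic reactions, all-grade anaphylaxis and gastrointestinal symptoms by arm, alongside the table of adverse events of grade 2 and above.
3. While editing, align the CTCAE version: Protocol 12.3.1 grades by 5.0 and Protocol 13.4.4 codes by 4.0, so the scale behind the floor is itself ambiguous.

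The cost is wording in both documents, one more table, and structured entry of mild reactions already in the diaries. The data entry is the real burden and could run to some hundreds of entries if reactions are as frequent as in the illustration. No visit, dose or clinical rule changes.
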